10.4 Reporting Serious Adverse Events

SAEs must be reported to Primus by telephone within 24 hours from the time the investigator first learns of them. This should be followed by a faxed report outlining the details of the event and the investigator's assessment of the severity and relationship of the event to the study agent. All SAEs will be reported on both the AE and SAE pages of the case report forms. In addition:

- A new SAE form must be completed and faxed to Primus within 24 hours
- Follow-up SAE forms must be completed and faxed to Primus whenever new information becomes available about the event
- A final SAE report must be completed and faxed to Primus when the event has resolved or
 its consequences have stabilized and all relevant information (including hospital records,
 laboratory and pathology reports, autopsy reports, etc.) have been received. It is the
 responsibility of the investigator to obtain copies of all relevant information in a timely
 manner.
- It is the responsibility of the investigator to determine the severity and causality of the SAE.
- The initial SAE and all subsequent reports must be retained in the subject's study file
 together with a telephone log of all contacts with Primus and the subject. These should be
 recorded at the time of the conversation, dated and signed by the investigator or his/her
 representative and should include the name of the person with whom the conversation was
 held.

Telephone contact should be made with: [name], Director Clinical Development [contact] [contact] [contact]

Primus will review all SAEs with the investigator and a decision will be made regarding the need for further action. Primus' primary concern will be subject safety, both for the subject having the event as well as for the other subjects in the study. If, after detailed review, it is determined that a subject safety issue exists, Primus will notify all investigators participating in any trial with the same study agent and may require one or more of the following:

- Discontinuation or suspension of the study
- Modification of the protocol
- Modification of the informed consent document to reflect additional risk(s) to be signed by current and future subjects
- Addition of newly discovered adverse events to the investigator's brochure

10.5 Follow-Up of Adverse Events

All adverse events, whether serious or non-serious, must be followed until resolution or stability. This follow-up may extend beyond the end of the study. Primus considers AE follow-up to be part of a study. Therefore, a study cannot be closed at an investigative site if an AE is outstanding.

Any serious AE occurring after the conclusion of a study must be reported to Primus if the investigator thinks the event *may* be causally related to the study agent.

10.6 Deaths

All deaths, regardless of cause, that occur between the time a subject signs an informed consent document and the final study visit or 30 days after the last dose of study product, whichever is longer, must be reported to Primus by telephone with a follow-up fax within 24 hours of the investigator becoming aware of the death. This applies whether or not the subject has received study product and whether or not the study product is thought to be causally related to the death.

It is the investigator's responsibility to obtain all relevant medical records and autopsy reports and forward them to Primus as soon as possible.

10.7 Reporting Safety Information to IRB

It is the responsibility of the investigator to notify his/her IRB of any unexpected or previously unknown risk to study subjects. This includes death from any cause and all SAEs. The investigator should make this report in accordance with the requirements of the IRB. The report should include any action taken after discussion of the SAE with Primus.

10.8 Managing Adverse Events

All AEs and SAEs should be medically managed according to the best medical standards available in the investigator's community. Except in the case of emergent treatment and routine care the management of the event should be discussed with Primus. Decisions regarding re-challenge with study product must be made in consultation with Primus.

10.9 Pregnancy

Although pregnancy is not considered to be an adverse event, Primus requires that investigators provide notice of any pregnancy in an active study subject or within 30 days of the last dose of study drug. Primus also requires investigators to provide follow-up information on the pregnancy and the health of the infant.

The informed consent document, signed by the patient, must contain information about the potential risks to pregnant women and/or to a fetus. Subjects must be advised to use contraception during and for 30 days after their participation in the study.

11. Ethical Considerations

This study will be conducted in accordance with the principles of the Declaration of Helsinki, ICH guidelines and Good Clinical Practices (GCPs) and US FDA regulations.

11.1 Informed Consent

All patients must read and sign the Research Subject Information and Consent Document (ICD) before they can be subjects in this research study. It is the investigator's responsibility to fully inform the patient about the procedures, risks and benefits of the study and to answer, in a manor clearly understandable to the patient, all the patient's questions. The ICD must be signed and dated by the patient, the investigator and a witness. A copy of the signed and dated ICD must be given to the subject. The IRB approved ICD must not be modified in any way from its original, IRB

approved form. The original copy of the ICD must be retained with the subject's study file and is subject to inspection by representatives of Primus and the regulatory agencies.

ICDs and all other written material distributed to subject during the study must be written in a language the subject understands.

A model informed consent form can be found on the IRB website.

11.1.1 Institutional Review Board (IRB)

Primus will assume responsibility for submitting the protocol and ICD to a central IRB. Before this can be done each investigator must submit the following to Primus:

- Signed and dated protocol signature page
- Completed, signed and dated FDA Form 1572
- Completed, signed and dated W-9 form
- Current curriculum vitae for investigator and all sub-investigators, signed and dated

If an investigator wishes to use an IRB other than that selected by Primus, he/she may do so after obtaining approval from Primus. In this case, the investigator will be responsible for all required submissions. Any changes to the model ICD must be first approved by Primus, in writing. The investigator must agree to all protocol amendments and, if necessary, make appropriate changes in the ICD. The IRB should be notified of any such changes and IRB approval must be sought for any changes involving subject safety. Serious or unexpected adverse events must be reported to the IRB within one week of their occurrence.

11.1.2 Subject Confidentiality

Subject identities should be protected at all times. This is the legal responsibility of the investigator. Subjects should be identified in study documents only by initials and study number on any document sent to Primus or a regulatory agency. Documents that are only for office use must be kept in strict confidence

Investigators must allow representatives of Primus or government regulatory agencies to inspect study records but the identity of the subjects should remain confidential.

12. Administrative and legal obligations

12.1 Pre-study Documentation

Before an investigator can begin screening subjects and before shipment of study agent can commence the investigator must complete and return the following to Primus:

Signed and dated protocol signature page

- Completed, signed and dated FDA Form 1572
- Copy of IRB approved ICD
- Copy of IRB approval letter for the study and ICD
- Membership list of IRB (usually supplied with approval letter)
- Current CVs of the investigator and all sub-investigators, signed and dated
- Signed and dated contract to conduct the study under the conditions and financial arrangements specified
- Name and contact information of person(s) responsible for the day to day management of the study

12.2 Protocol Amendments

Protocol amendments may be made only by Primus. The investigator's IRB must be informed of any amendments that may affect subject safety or the conduct of the study. The IRB must issue a letter of approval of such amendments. The investigator must keep the original letter in the study's regulatory binder and forward a copy of the letter to Primus.

12.3 Study Termination

Both the investigator and Primus have the right to terminate their participation in the study. If this is done by the investigator he/she must provide a detailed explanation of the action to Primus and the IRB and a copy of this account must be retained with the regulatory file.

12.4 Case Report Forms (CRFs)

Primus will provide investigators with sets of NCR paper CRFs bearing information identifying the study site and the principle investigator. All data obtained during the course of the study will be recorded on the CRFs. The CRFs should be reviewed on site for completeness by the investigator or his/her representative. The original will be forwarded to Primus and a copy will remain with the subject's study data file.

CRFs contain the critical study data and are the basis from which results are tabulated, analyses performed and final reports made. Therefore, it is essential that data recorded on the CRFs be legible, complete and accurate. Forms should be typed or completed in black ball point ink. Corrections should be made by placing a single line through the error, adding the correct data then initialing and dating the correction. Under no circumstances should the original entry be erased, overwritten or obscured by white-out or some other method. CRFs should contain only subject initials and study number. Names or other identifying information should not appear. All data points must be answered. If the information is unknown or unavailable the terms "NA" (not available), "ND" (not done), "SU" (subject unable) or "DP" (data pending) may be used.

Primus regards all information obtained from the conduct of this study as confidential. If an investigator wishes to publish or present in oral or written form all or part of the data obtained during the study he/she must first submit a complete copy of such presentation to the director of Clinical Investigation for review and approval. This submission must occur no later than sixty (60) days before the anticipated date of presentation. The investigator will be required to incorporate any suggestions made by Primus consistent with its right to

protect the confidentiality of the information.

16. Statistical considerations

This is a pilot, exploratory case study designed to inform development of a formal RBCDB clinical trial. As such, only those variables clearly shown to be affected by the study treatment will be incorporated into the formal trial.

Descriptive statistics will be presented for all relevant variables including demographic variables such as age, sex, weight and BMI for each group. Descriptive statistics for baseline and endpoint values for all study variables, including weight, BMI leg circumference, short WOMAC, investigator Likert and all subject reported outcomes per section 4.2 will also be presented. Data from baseline and final visit will be compared by Student's t-test (paired). P values </= 0.05 will be considered of significance.

17. References

Colleridge-Smith PD. Micronized purified flavonoid fraction and the treatment of chronic venous insufficiency: microcirculatory mechanisms. Microcirc. 2000.7:S35-40.

Herbst KL. Medications and Supplements. (2019, March 18). Retrieved from https://treat.medicine.arizona.edu/treatments-therapies/

Herbst KL. Rare adipose disorders (RADs) masquerading as obesity. Acta Pharmacologica Sinica. 2012.33:155-72.

its use in chronic venous insufficiency, venous ulcers and haemorrhoids, Drugs. 2003.63:71100.

Lyseng-Williamson KA, Perry CM. Micronized purified flavonoid fraction: a review of

Appendix I

The World Medical Association Declaration of Helsinki

World Medical Association Declaration of Helsinki: Recommendations Guiding Medical Doctors in Biomedical Research Involving Human Subjects

Adopted by the 18th World Medical Assembly, Helsinki, Finland, 1964 and as last revised by the World Medical Assembly in Seoul, Korea 2008

Introduction

It is the mission of the physician to safeguard the health of the people. His or her knowledge and conscience are dedicated to the fulfillment of this mission.

The Declaration of Geneva of the World Medical Association binds the physician with the words, "The health of my patient will be my first consideration," and the International Code of Medical Ethics declares that, "A physician shall act only in the patient's interest when providing medical care which might have the effect of weakening the physical and mental condition of the patient."

The Purpose of biomedical research involving human subjects must be to improve diagnostic, therapeutic and prophylactic procedures and the understanding of the etiology and pathogenesis of disease.

In current medical practice most diagnostic, therapeutic or prophylactic procedures involve hazards. This applies especially to biomedical research.

Medical progress is based on research which ultimately must rest in part on experimentation involving human subjects.

In the field of biomedical research a fundamental distinction must be recognized between medical research in which the aim is essentially diagnostic or therapeutic for a patient, and medical research, the essential object of which is purely scientific and without implying direct diagnostic or therapeutic value to the person subjected to the research.

Special caution must be exercised in the conduct of research which may affect the environment, and the welfare of animals used for research must be respected.

Because it is essential that the results of laboratory experiments be applied to human beings to further scientific knowledge and to help suffering humanity, the World Medical Association has prepared the following recommendations as a guide to every physician in biomedical research involving human subjects. They should be kept under review in the future. It must be stressed that the standards as drafted are only a guide to physicians all over the world. Physicians are not relieved from criminal, civil and ethical responsibilities under the laws of their own countries.

I. Basic Principles

- 1. Biomedical research involving human subjects must conform to generally accepted scientific principles and should be based on adequately performed laboratory and animal experimentation and on a thorough knowledge of the scientific literature.
- 2. The design and performance of each experimental procedure involving human subjects should be clearly formulated in an experimental protocol which should be transmitted for consideration, comment and guidance to a specially appointed committee independent of the investigator and the sponsor provided that this independent committee is in conformity with the laws and regulations of the country in which the research experiment is performed.
- 3. Biomedical research involving human subjects should be conducted only by scientifically qualified persons and under the supervision of a clinically competent medical person. The responsibility for the human subject must always rest with a medically qualified person and never rest on the subject of the research, even though the subject has given his or her consent.
- 4. Biomedical research involving human subjects cannot legitimately be carried out unless the importance of the objective is in proportion to the inherent risk to the subject.
- 5. Every biomedical research project involving human subjects should be preceded by careful assessment of predictable risks in comparison with foreseeable benefits to the subject or to others. Concern for the interests of the subject must always prevail over the interests of science and society.
- 6. The right of the research subject to safeguard his or her integrity must always be respected. Every precaution should be taken to respect the privacy of the subject and to minimize the impact of the study on the subject's physical and mental integrity and on the personality of the subject.
- 7. Physicians should abstain from engaging in research projects involving human subjects unless they are satisfied that the hazards involved are believed to be predictable. Physicians should cease any investigation if the hazards are found to outweigh the potential benefits.
- 8. In publication of the results of his or her research, the physician is obliged to preserve the accuracy of the results. Reports of experimentation not in accordance with the principles laid down in this Declaration should not be accepted for publication.
- 9. In any research on human beings, each potential subject must be adequately informed of the aims, methods, anticipated benefits and potential hazards of the study and the discomfort it may entail. He or she should be informed that he or she is at liberty to abstain from participation in the study and that he or she is free to withdraw his or her consent to participation at any time. The physician should then obtain the subject's freely-given informed consent, preferably in writing.
- 10. When obtaining informed consent for the research project the physician should be particularly cautious if the subject is in a dependent relationship to him or her or may consent under duress. In that case the informed consent should be obtained by a physician who is not engaged in the investigation and who is completely independent of this official relationship.
- 11. In case of legal incompetence, informed consent should be obtained from the legal guardian in accordance with national legislation. Where physical or mental incapacity makes it impossible to obtain informed consent, or when the subject is a minor, permission from the responsible relative replaces that of the subject in accordance with national legislation.
 - Whenever the minor child is in fact able to give a consent, the minor's consent must be obtained in addition to the consent of the minor's legal guardian.
- 12. The research protocol should always contain a statement of the ethical considerations involved and should indicate that the principles enunciated in the present Declaration are complied with.

II. Medical Research Combined with Professional Care (Clinical Research)

- 1. In the treatment of the sick person, the physician must be free to use a new diagnostic and therapeutic measure, if in his or her judgment it offers hope of saving life, reestablishing health or alleviating suffering.
- 2. The potential benefits, hazards and discomfort of a new method should be weighed against the advantages of the best current diagnostic and therapeutic methods.
- 3. In any medical study, every patient--including those of a control group, if any--should be assured of the best proven diagnostic and therapeutic method.
- 4. The refusal of the patient to participate in a study must never interfere with the physician-patient relationship.
- 5. If the physician considers it essential not to obtain informed consent, the specific reasons for this proposal should be stated in the experimental protocol for transmission to the independent committee (I,2).
- 6. The physician can combine medical research with professional care, the objective being the acquisition of new medical knowledge, only to the extent that medical research is justified by its potential diagnostic or therapeutic value for the patient.

III. Non-Therapeutic Biomedical Research Involving Human Subjects (Non-Clinical Biomedical Research)

- 1. In the purely scientific application of medical research carried out on a human being, it is the duty of the physician to remain the protector of the life and health of that person on whom biomedical research is being carried out.
- 2. The subjects should be volunteers--either healthy persons or patients for whom the experimental design is not related to the patient's illness.
- 3. The investigator or the investigating team should discontinue the research if in his/her or their judgment it may, if continued, be harmful to the individual.
- 4. In research on man, the interest of science and society should never take precedence over considerations related to the well-being of the subject.

Appendix II

Acceptable Contraceptive Measures

- 1- Oral contraceptives
- 2- Depo Provera
- 3- norplant implants
- 4- Intra-uterine device
- 5- Tubal ligation
- 6- Vasectomy
- 7- Condom plus diaphragm
- 8- condom plus contraceptive sponge or spermicidal jelly

Appendix III

Diagnostic Features of Lipedema

From Wold 1951; modified by Herbst 2012

- Women
- Usual onset at puberty, pregnancy or menopause
- Symmetrical adipose hypertrophy of lower extremities, sparing trunk and feet, with sharp demarcation at ankles (cuffing). Upper extremities may or may not be involved.
- Negative Stemmer sign
- Easy Bruising
- Minimal pitting edema
- Pain, often spontaneous, tenderness on palpation
- No response to leg elevation or weight loss

APPENDIX V: Body Mass Index Table

To use the table, find the appropriate height in the left-hand column labeled Height. Move across to a given weight. The number at the top of the column is the BMI at that height and weight. Pounds have been rounded off.

DMI	19	111111 15	the Biv		23	24	25	Touri	27	occii i	29		31	32	33	34	3
BMI	19	20	21	22	23	24	25	26	21	28	29	30	31	32	33	34	2
Height (inches)	Body Weight (pounds)																
58	91	96	100	105	110	115	119		129	134	138	143	148	153	158	162	16
59	94	99	104	109	114		124		133	138	143	148	153	158		168	17
60	97	102	107	112	118	123	128	133	138	143	148	153	158	163	168	174	17
61	100	106	111	116	122	127	132	137	143	148	153	158	164	169	174	180	18
62	104	109	115	120	126	131	136	142	147	153	158	164	169	175	180	186	19
63	107	113	118	124	130	135	141	146	152	158	163	169	175		186	191	19
64	110	116	122	128	134	140	145	151	157	163	169	174	180	186	192	197	20
65	114	120	126	132	138	144	150		162	168	174	180	186	192	198	204	21
66	118	124	130	136	142	148	155	161	167	173	179	186	192			210	21
67	121	127	134	140	146	153	159	166	172	178	185	191	198	204	211	217	22
68	125	131	138	144		158	164	171	177	184	190	197	203	210		223	23
69	128	135	142	149	155	162	169		182	189	196		209	216		230	23
70	132	139	146	153	160	167	174	181	188	195	202		216	222	229	236	24
71	136	143	150		165	172	179	186	193	200	208	215	222	229	236	243	25
72	140	147	154	162		177	184	191	199	206	213	221	228	235	242	250	25
73	144	151	159	166	174	182			204	212	219		235	242	250	257	26
74		155		171	179	186	194	202	210	218	225	233	241	249	256	264	27
75	152	160	168	176		192	200	208	216	224	232	240	248	256	264	272	27
76		164	172	180	189	197	205	213	221	230	238	246	254	263	271	279	28

Appendix VI Blood Sample Processing

I. FREEZE PLASMA WITHIN ONE (1) HOUR OF DRAWING

- II. Shipping boxes and exterior labeling will be provided.
- III. Samples will be shipped in 2 separate batches.
- IV. Draw and process as directed below.
 - 1. Complete one lab requisition for each draw; v1 and v4
 - 2. Draw 10 ml blood into lavender top K2 EDTA tube
 - 3. Centrifuge for 15 minutes at 5000 rpm
 - 4. Decant or pipette plasma into two (2) 3 ml cryovials
 - 5. Label each cryovial with cryo-pen:

a. Subject initials Ex: ABC or A-C

b. 3-digit study number Ex: site 1 subject 4 = 104 (Site # = 1-digit, Subj # = 2-digits)

c. Date and time of draw Ex: mm/dd/yy 9:05 am or 1:20 pm

d. Visit number = 1 or 4 Ex: v1 or v4

6. Store at -70° F within 1 hour of drawing

At study completion:

- 1. Retain one sample for each subject at -70° F
- 2. Ship one sample in dry ice to:

Attn: [name] Laboratory Chemical Engineering Department Northeastern University [name]

3. After arrival of first shipment is confirmed, ship second batch.

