2.0 Study objectives

This exploratory case study is designed to gain preliminary information via a uniform protocol regarding the clinical effects of Vasculera in patients with lipedema and the possible role of the glycocalyx as a physiological target for Vasculera activity. It is anticipated that the results of this case study will inform the development of a formal randomized, double-blind, placebo controlled trial.

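### Glycocalyx vials are labelled with visit and draw date, and no masking step is planned, so the laboratory can tell pre-treatment from on-treatment samples; coding them would be a cheap improvement

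*Protocol*

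**What the plan says.** Protocol Appendix VI (Blood Sample Processing) lists what goes on each cryovial: subject initials, then "b. 3-digit study number Ex: site 1 subject 4 = 104", then "c. Date and time of draw Ex: mm/dd/yy 9:05 am or 1:20 pm", then "d. Visit number = 1 or 4 Ex: v1 or v4". For paperwork it asks the site to "Complete one lab requisition for each draw; v1 and v4". Each draw is split into two cryovials. Under the line "At study completion", one sample is retained and one is shipped on dry ice to a university laboratory, with a second shipment once the first has arrived.

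Protocol Section 4.0 describes an open-label study of three months, and Section 3.0 gives all subjects the product. Section 2.0 names two things to learn about. One is the clinical effects; the other is "the possible role of the glycocalyx as a physiological target for Vasculera activity". Protocol Section 4.2 and SAP Section 1.3 class the plasma markers as exploratory. SAP Section 2.5 analyses their change from baseline to month 3 by a paired t-test or a Wilcoxon signed rank test, and SAP Section 2.1 sets a two-sided alpha of 0.05.

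Neither document mentions coding or relabelling of samples, a masked laboratory, randomised assay order, or assaying a subject's two samples together.

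**The concern.** With one treated group, the visit number is the treatment state. Initials and study number let the assayer pair a subject's two vials, and visit number and draw date each show which came first. If re-runs, dilutions or out-of-range values involve judgement at the bench, knowing the visit could affect that judgement. Any such effect would enter the month 3 minus baseline difference directly, and there is no control arm in which it would show.

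Exploratory status limits what is at stake but does not remove it. The markers are the only measure of the mechanistic objective. Protocol Section 16 also says that the formal trial will take forward only variables clearly shown to be affected by treatment, so a spurious marker change could influence that trial's design.

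**Working it through.** **1. What the label reveals, set against what is tested.**
- Label (Appendix VI): initials and study number identify the pair; date, time and visit identify the order.
- Test (SAP Section 2.5): value at month 3 minus value at baseline, within subject.
- The label therefore identifies both terms of the tested difference. Removing the visit number alone would not mask the order, because the draw date also gives it.

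**2. Whether masking is feasible.** Shipment takes place at study completion, so both samples of a subject who completes exist before either is assayed. With 30 subjects, 2 draws and 2 cryovials per draw, there are 30 × 2 × 2 = 120 vials if nobody drops out. If one vial per draw is assayed, that is 60 samples for each of the two markers.

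**3. Other outcomes.** The rest are self-ratings, an investigator rating, and clinic measurements at known visits (Protocol Sections 6.2 to 6.5). Weight and leg circumference could be taken by staff masked to visit and earlier readings, but that needs added clinic procedures. The markers are measured off site on stored samples, so they are the easiest to mask.

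**4. Illustration of scale.** The plan has no figure to reproduce: SAP Section 1.1 states that no formal sample size calculation was done. The documents give no SD of change and no assay precision, so the shift b below is an assumption, in units of the SD of the paired change.

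A systematic shift b in the month 3 readings moves the paired t statistic by b × √n. With n = 30, √30 = 5.48. The rejection rate when there is no true change comes from the noncentral t distribution with 29 degrees of freedom, and simulation confirmed the non-zero rows.

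| Assumed b | Shift in t (b × 5.48) | False-positive rate, n = 30 | Same, n = 24 |
|---|---|---|---|
| 0 | 0 | 5% | 5% |
| 0.1 | 0.55 | 8.3% | 7.6% |
| 0.2 | 1.10 | 18.5% | 15.6% |
| 0.3 | 1.64 | 35.6% | 29.1% |

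The n = 24 column assumes that 20% of subjects lack a usable pair (30 × 0.8 = 24). For reference, an observed mean change of 0.373 SD reaches p = 0.05 at n = 30. The same arithmetic holds for a shift from any source. It shows how sensitive the test is and is not evidence that a shift would occur.

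**The case against.** The strongest reply is that nothing in the documents shows a bias, and this stands in several respects.

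- A reader might infer that the laboratory would know which way the sponsor hopes the markers will move. The documents do not support that. They never say whether syndecan-1 or heparan sulfate should rise or fall, the tests are two-sided, and nothing says what the laboratory will be told.
- A reader might infer that the markers are the only outcome that could be masked. They are not, since weight and circumference could be masked with more effort.
- A reader might infer that the assayer will certainly be unmasked. Appendix VI is a site instruction and does not rule out recoding on receipt, and the requisition form is not shown. But no such step is planned, and the vial label alone is enough to reveal the visit.
- The assay and its re-run and dilution rules are not described, so the room for operator influence is unknown. SAP Section 3.3 has outliers checked against source documents and kept if not erroneous. That helps, but it does not reach decisions made in the laboratory before results are reported.
- Masking would not repair the larger weaknesses of the comparison. There is no control group, and v1 samples are stored longer than v4 samples.
- Explicit visit labels guard against mix-ups. With a random suffix, a swap within a pair reverses the sign of that subject's change and cannot be seen at the laboratory. A requisition copy kept at the site would not catch it if vial and form carry the same wrong code.

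The last point concerns how the fix is built and is not a reason to leave the labels as they are. The others limit the size of the claim.

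**Conclusion.** The point holds as a cheap improvement. As the plan is written, the outside laboratory can tell pre-treatment from on-treatment samples in an open-label, single-arm study, and no masking step appears in either document. This affects the sole measure of one of the two stated objectives, in an outcome that is exploratory.

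The documents do not show that the marker results will be biased, and the size or direction of any bias cannot be derived from them. The rates of 8.3% to 35.6% rest on assumed shifts of 0.1 to 0.3 SD and are illustrative only. The case for changing the labels rests on the safeguard being easy to add before shipment, not on a demonstrated error.

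**What to change.** In Appendix VI, replace the labelling step:

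- Vials, and the laboratory's copy of the requisition, carry only a neutral pre-printed code: a subject-pair number plus a suffix allocated at random to v1 and v4. No visit, date or initials appear.
- The sponsor generates the code list in advance.
- The site records the code against visit and draw time on a log at the time of the draw. A second check against the list is made before shipment.
- The laboratory assays both samples of a subject in the same run, in random order, and returns locked results before the key is released.

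Add one matching sentence to SAP Section 2.5. While Appendix VI is open, clarify the line "Samples will be shipped in 2 separate batches". It reads most naturally as duplicate vials shipped in turn. If it meant v1 in one batch and v4 in the other, visit would be confounded with batch and the same-run rule could not be met unless both batches were held and assayed together.

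The cost is pre-printed labels, a code list, a log and one check before shipment, with no extra visit or blood sample. The downside is the small risk of a within-pair code swap, which the log and the pre-shipment check must control.
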